### 2.6.3 Modified Intent-to-Treat Analysis Population

The Modified ITT population is defined as all randomized subjects who received at least one study stent according to their treatment assignment.

### 2.6.4 Analysis Sets for BIOFLOW-II and BIOFLOW-IV (Bayesian Analysis Population)

Only BIOFLOW-II and BIOFLOW-IV randomized subjects who satisfy BIOFLOW-V clinical and angiographic inclusion/exclusion criteria and who have sufficient follow-up data (at least 330 days of follow-up or experience the primary endpoint) will be included in the BIOFLOW V Bayesian analysis.

The subjects in BIOFLOW-II and BIOFLOW-IV who meet the inclusion/exclusion criteria of BIOFLOW-V will be determined before the BIOFLOW V database is locked and will be done by an independent statistician without the knowledge of any of the outcome data.

A sensitivity analysis of the ITT primary endpoint analysis will be performed by including all BIOFLOW-II and BIOFLOW-IV randomized subjects who have sufficient follow-up data (at least 330 days of follow-up or experience the primary endpoint) whether or not the subjects satisfy the BIOFLOW-V inclusion/exclusion criteria.

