8.1. Prior Data

The Orsiro clinical trial program includes BIOFLOW-II, BIOFLOW-IV and BIOSCIENCE, three randomized controlled trials in which subjects were randomized to the Orsiro stent against the Xience Prime™ or Xience Xpedition™ stents. A brief description of these trials is provided in Section 3.5. The inclusion and exclusion criteria for BIOFLOW-II and BIOFLOW-IV are nearly identical to those proposed for BIOFLOW-V, whereas the inclusion and exclusion criteria in BIOSCIENCE were more liberal to allow enrollment of a broadly inclusive real world population. We propose to use data from the BIOFLOW-II and BIOFLOW-IV trials prospectively using a Bayesian approach in the final non-inferiority analysis of the BIOFLOW-V study. A summary of the comparison of the study design of BIOFLOW-II and -IV trials along with the proposed BIOFLOW-V study can be found in Table 8-1. The current status of the studies is as follows:

- BIOFLOW-II – Enrollment into the trial was completed and 12-month results are available. A total of 298 subjects were randomized to receive the Orsiro stent and 154 were randomized to receive the Xience Prime™ stent. Of them, 287 Orsiro subjects and 148 Xience subjects completed their 12-month follow-up.
- BIOFLOW-IV - Enrollment into the trial is still ongoing and it is anticipated that 370 Orsiro subjects and 185 Xience Prime™/Xpedition™ subjects will be contributed from this trial.

To ensure the validity of data from subjects across trials, the following measures will be taken:

- Only subjects that meet all BIOFLOW-V clinical and angiographic eligibility criteria will be included.
- Evaluation of the 12-month TLF rate (a primary endpoint in the BIOFLOW-V trial and a secondary endpoint in the BIOFLOW-II and BIOFLOW-IV trials) will be performed in a uniform fashion, using a consistent set of definitions and similar follow-up schedule:
 - The measurement schedule of cardiac enzymes is similar in all trials: cardiac enzymes are collected once within 6-24 hours post index procedure. While all trials mandated collection of CK and CKMB, the BIOFLOW-II also mandated measurement of troponin. The BIOFLOW-IV and BIOFLOW-V trials allow measurement of troponin if CK and CKMB are not used. To address the differences in the collection of cardiac enzymes between the three trials, a uniform definition of peri-procedural MI that is based on CK and CKMB levels (with troponin levels used only in the absence of CK and CKMB) will be utilized.

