## 2.8 Handling of Missing Data in the Analysis of Primary Endpoint

Every effort will be undertaken to limit premature discontinuations and ascertain completeness of data collection. The following analysis strategies will be adopted to handle missing data with results compared for consistency prior to carrying out the above analysis:

- 1) Only subjects who experienced the primary endpoint (TLF at 12 months) or who had appropriate follow-up (at least 330 days post baseline, given the 30-day visit window allowed around the 12-month visit) will be included in the analysis.
- 2) All subjects will be included in the analysis set including data for subjects missing primary endpoint status due to not experiencing the event and not reaching at least 330 days of follow-up. Data for these subjects will be included as 'NA'. Bayesian method will be used for the imputation. A model will be used for the event probabilities:

$$Y[i, j, k] \sim \text{dbern}(p[i, j, k])$$

with

$$\text{logit}(p[i, j, k]) = \beta * X[k] + \text{logit}(p[i, j])$$

where  $X[k]$  are predictors values for subject  $k$ . A noninformative prior will be assumed on the slope parameters  $\beta$  and similarly to the analysis of the primary endpoint, bias will be assumed between TLF rates in different studies.

The following variables will be included in the model as covariates:

- Age (>75, <=75)
- Gender
- Diabetes
- Lesion length (>26 mm, <=26mm)
- RVD (>2.75mm, <=2.75mm)

- 3) Time to event analysis using a Bayesian time to event exponential regression analysis. The protocol specifies that time to event analysis using a Bayesian Cox regression analysis will be performed as a sensitivity analysis but subsequently we determined that an exponential regression is better for allowing incorporating a bias term between the log hazard rates in BIOFLOW-V and BIOFLOW II and BIOFLOW-IV. For each study, a separate hazard ratio comparing Xience to Orsiro stent will be included. Similar to the method proposed as a primary method, a bias will be assumed between the log hazard of BIOFLOW-II or BIOFLOW-IV and the log hazard of the BIOFLOW-V.

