### Model

For ease of presentation we assume that no censoring occurs. The below model will accommodate censoring.

For a subject  $i$  in the BIOFLOW-V study, if  $Y_{X,i}^V$  is the time to event, let

$$Y_{X,i}^V \sim \text{exponential}(\lambda_X^V) \quad \text{and} \quad Y_{O,i}^V \sim \text{exponential}(\lambda_O^V)$$

be the distributions of the time (years) to event in the Xience and Orsiro groups, respectively. The values  $\lambda_X^V$  and  $\lambda_O^V$  are the hazards in the Xience and Orsiro groups.

*Evidence from BIOFLOW-IV study:* It is first discounted using the discount factor  $a^{IV}$ . The discounted data are then assumed to follow exponential distributions with hazard rates  $\lambda_X^{IV}$  and  $\lambda_O^{IV}$  in the Xience and Orsiro groups, respectively. For a subject  $i$  in the BIOFLOW-IV study, if  $Y_{X,i}^{IV}$  is the time to event, let

$$Y_{X,i}^{IV} \sim \text{exponential}(\lambda_X^{IV}) \quad \text{and} \quad Y_{O,i}^{IV} \sim \text{exponential}(\lambda_O^{IV})$$

A bias term is assumed to link the TLF hazard rates in BIOFLOW-V and BIOFLOW-IV in each treatment group

$$\bullet \quad \log(\lambda_X^V) = \log(\lambda_X^{IV}) + \delta_X^{IV} \quad \text{and} \quad \log(\lambda_O^V) = \log(\lambda_O^{IV}) + \delta_O^{IV}$$

*Evidence from BIOFLOW- II study:* It is first discounted using the discount factor  $a^{II}$ . The discounted data are then assumed to follow Exponential distributions with hazard rates  $\lambda_X^{II}$  and  $\lambda_O^{II}$  in the Xience and Orsiro groups, respectively,

$$Y_{X,i}^{II} \sim \text{exponential}(\lambda_X^{II}) \quad \text{and} \quad Y_{O,i}^{II} \sim \text{exponential}(\lambda_O^{II})$$

A bias term is assumed to link the TLF rates in BIOFLOW-II and BIOFLOW-V in each treatment group.

$$\log(\lambda_X^V) = \log(\lambda_X^II) + \delta_X^II \text{ and } \log(\lambda_O^V) = \log(\lambda_O^II) + \delta_O^II$$

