### Prior distribution

The bias terms are assumed to follow a normal distribution with mean 0 and standard deviation  $\tau_1$  and  $\tau_2$ .

$$\delta_X^II \sim \text{Normal}(0, \tau_1) \text{ and } \delta_O^II \sim \text{Normal}(0, \tau_1)$$

$$\delta_X^{IV} \sim \text{Normal}(0, \tau_2) \text{ and } \delta_O^{IV} \sim \text{Normal}(0, \tau_2)$$

As with primary endpoint analysis, a value of 0.3 will be assumed for both  $\tau_1$  and  $\tau_2$ . Non-informative prior distributions are assumed for TLF rates in the BIOFLOW-V study

$$\lambda_X^V \sim \text{gamma}(0.1, 0.1) \text{ and } \lambda_O^V \sim \text{gamma}(0.1, 0.1)$$

The non-inferiority condition will be expressed in terms of 1-year TLF rates in the BIOFLOW-V study as with the primary hypothesis

$$P(H_A | \text{Data}) = P(\pi_X^V - \pi_O^V > -\delta | \text{Data}) > \pi^*$$

where the 12-month TLF rates will be calculated as

$$\pi_X^V = 1 - \exp(-\lambda_X^V) \text{ and } \pi_O^V = 1 - \exp(-\lambda_O^V)$$

- 4) A tipping point analysis will be carried out. Here, it is assumed that for all Xience patients with missing primary endpoint (12-month TLF) status, TLF did not occur. For Orsiro patients with missing data, it will be first assumed that the primary endpoint of TLF occurred for exactly one such patient; then the primary analyses will be re-run to assess if non-inferiority is met under this assumption. Then it will be assumed the primary endpoint occurred for exactly two Orsiro patients with missing data, and the primary non-inferiority analysis will be rerun. The process will continue sequentially in this manner until all Orsiro patients with missing data are considered to have met the primary endpoint of TLF. Of interest is the “tipping point”, or i.e., the number of imputed Orsiro TLFs where non-inferiority is not met in this analysis.

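### SAP 2.6.4 and SAP 2.8 disagree on whether BIOFLOW-II/IV subjects who left event-free before day 330 enter the missing-data analyses; read literally, 2.6.4 leaves drop-out in the borrowed data out of the tipping point

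*SAP*

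**What the plan says.** SAP 2.6.4 defines the historical analysis set. A BIOFLOW-II or BIOFLOW-IV subject must meet BIOFLOW-V eligibility, and only those "who have sufficient follow-up data (at least 330 days of follow-up or experience the primary endpoint) will be included in the BIOFLOW V Bayesian analysis". One sensitivity analysis in the same section lifts the eligibility condition but repeats the follow-up condition.

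SAP 2.8 lists four strategies for missing primary-endpoint status:

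- Item 1 is the complete-case rule: an event, or at least 330 days.
- Item 2 states "All subjects will be included in the analysis set including data for subjects missing primary endpoint status". These subjects are entered as NA, in a model where "bias will be assumed between TLF rates in different studies".
- Item 3 is an exponential time-to-event model written for all three trials. It says "The below model will accommodate censoring".
- Item 4 is the tipping point. Missing Xience subjects count as event-free. Missing Orsiro subjects are switched to TLF one at a time "until all Orsiro patients with missing data are considered to have met the primary endpoint of TLF". The text does not restrict this to BIOFLOW-V.

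Protocol 8.1 filters historical subjects on eligibility only. It reports for BIOFLOW-II that "287 Orsiro subjects and 148 Xience subjects completed their 12-month follow-up", out of 298 and 154 randomized.

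**The concern.** The follow-up condition in 2.6.4 depends on outcome: a historical subject who leaves early is kept after a TLF event and removed without one. The selection made without knowledge of outcome, described in the same section, covers the eligibility criteria only.

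Items 2 to 4 of SAP 2.8 exist to test what happens when complete-case selection is dropped. If 2.6.4 fixes the historical set for every analysis, that selection is already built into the borrowed data before items 2 to 4 start. Two programmers working from this SAP could build different historical sets.

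The non-inferiority verdict rests on all three trials together. A tipping point that varies only BIOFLOW-V drop-out tests part of the evidence. A censored time-to-event analysis should not remove event-free person-time because follow-up was short.

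**Working it through.** **Inputs.** From SAP 2.3 to 2.5: TLF 7% in both arms, margin 3.85 points, success threshold 0.975, historical weights 0.7 (BIOFLOW-II) and 0.8 (BIOFLOW-IV), bias SD 0.3 (taken on the log-odds scale), Beta(1,1) prior, 800 + 400 evaluable subjects, about 10% loss. From Protocol 3.5 and 8.1: BIOFLOW-II rates of 6.5% and 8.0%; planned BIOFLOW-IV numbers of 370 and 185.

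**Derived or assumed.**
- BIOFLOW-II events: 0.065 × 287 ≈ 19 Orsiro; 0.080 × 148 ≈ 12 Xience.
- BIOFLOW-II non-completers: 298 − 287 = 11 (3.7%) and 154 − 148 = 6 (3.9%). These are upper bounds on the subjects removed, since a non-completer with an event is kept.
- BIOFLOW-IV loss is not in the documents. I use 0%, 3.7% (14 and 7 subjects) and 10% (37 and 18 subjects), with TLF about 7%.
- All historical subjects are taken as eligible for BIOFLOW-V, and the discount as a power weight on the counts.

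**The plan's own figure.** With BIOFLOW-II held at its reported result and BIOFLOW-IV simulated, the rebuilt model gives 88.9% power against the stated 89.6%. Type I error is 3.9/3.4/4.4% against the stated 4.0/3.3/4.2%. Simulating BIOFLOW-II at 7% in both arms gives 85.9%. Without borrowing, power is 74.1%, so the historical data carry real weight.

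**Item 2.** For a missing binary outcome the likelihood contribution is p + (1 − p) = 1. Restoring historical leavers as NA leaves the posterior of the TLF rates essentially unchanged.

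**Item 3.** For BIOFLOW-II, hazard λ = events / person-years and 12-month rate = 1 − exp(−λ). Assume events occur at 0.3 years on average and leavers are censored at c years.
- Orsiro, leavers deleted: 19 / (268 + 0.3 × 19) = 19 / 273.7, rate 6.71%. With 11 leavers at c = 0.85: 19 / 283.05, rate 6.49%. At c = 0.1: 6.68%.
- Xience, leavers deleted: 12 / (136 + 0.3 × 12) = 12 / 139.6, rate 8.24%. With 6 leavers at c = 0.85: 12 / 144.7, rate 7.96%. At c = 0.1: 8.20%.

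Deletion therefore overstates the rate by 0.03 to 0.21 points (Orsiro) and 0.03 to 0.28 points (Xience), before discounting and the bias term. Which arm moves more depends on when subjects left, so there is no clear direction between arms.

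**Item 4.** BIOFLOW-V is set at 889 and 445 randomized, 89 and 45 missing, with 56/800 and 28/400 TLF observed. The entry is the number of BIOFLOW-V Orsiro subjects imputed as TLF at which non-inferiority fails. In the last two columns, Xience historical leavers count as event-free.

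| BIOFLOW-IV loss (assumed) | Historical leavers excluded | Historical Orsiro leavers fail at the same fraction as in BIOFLOW-V | All historical Orsiro leavers fail |
|---|---|---|---|
| 0% | 17-18 | 17 | 14-15 |
| 3.7% | 17-18 | 16 | 10-11 |
| 10% | 17-18 | 15 | 5-6 |

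The one-event ranges reflect small differences in set-up; at 17 the posterior probability lies almost on 0.975. Over five BIOFLOW-V scenarios (Orsiro/Xience 5/7, 6/7, 7/7, 6/8 and 8/8%), with BIOFLOW-IV loss of 3.7% or 10%, the tipping point falls by 7 to 12 events under the extreme rule and by 1 to 5 under the same-fraction rule.

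**The case against.** The strongest reply is that 2.6.4 describes only the base-case historical set. Its 330-day rule matches item 1 of SAP 2.8, and items 2 to 4 can be read as relaxing it for all three trials. On that reading nothing is excluded from the sensitivity analyses. This reading is tenable, so a reader who infers that historical leavers are removed from every Bayesian analysis, or that items 2 to 4 are blind to them, goes further than the text allows. It does not settle the matter, because 2.6.4 is the specific population definition, is worded exclusively, and repeats the filter in its own sensitivity analysis.

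The second reply concerns size. A reader might infer that the tipping point really drops from 18 to 6. That requires every historical Orsiro leaver to fail first, counts only BIOFLOW-V imputations afterwards, and uses a 10% BIOFLOW-IV loss borrowed from BIOFLOW-V planning. If all imputed Orsiro events are counted, that ordering gives totals of 14 + 11 = 25, 11 + 25 = 36 and 6 + 48 = 54, which is above 17-18. Under the same-fraction rule, the share of missing Orsiro subjects that must fail moves from 17/89 to 18/89 (19-20%) to 17/89, 16/89 and 15/89 (19%, 18% and 17%). This objection stands: the like-for-like loss of robustness is small.

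It is also fair that the tipping point has no pass/fail threshold, and that no effect on the primary success rule follows.

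**Conclusion.** The conflict between SAP 2.6.4 and SAP 2.8 is real and should be resolved before analysis. If 2.6.4 governs:

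- Item 2 is numerically unaffected.
- Item 3 uses outcome-selected historical person-time. The error is small, at most about 0.2 to 0.3 points in BIOFLOW-II, and affects both arms.
- Item 4 does not test drop-out in the borrowed data. The tipping point of 17-18 becomes 15-17 under a like-for-like rule. It is much lower only in the extreme case.

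The extreme case is a stress test and not an expected bias. If missing historical Orsiro subjects had double the risk, the posterior difference would move by about 0.03 to 0.11 points, or 0.03/3.85 = 1% to 0.11/3.85 = 3% of the margin. The documents do not support a claim that the primary result is biased.

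The sizes depend on the assumed BIOFLOW-IV loss, on the BIOFLOW-II non-completers as upper bounds, and on 7% observed TLF in BIOFLOW-V. The direction of the tipping-point effect held in all five scenarios.

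**What to change.** In SAP 2.6.4, limit the condition of 330 days or an event to item 1 of SAP 2.8. For items 2 to 4, define the historical set as all randomized BIOFLOW-II and BIOFLOW-IV subjects who meet BIOFLOW-V eligibility: NA in item 2, censored at last contact in item 3.

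Report the number of BIOFLOW-II and BIOFLOW-IV subjects with missing 12-month status by arm. Report the tipping point with and without historical leavers, and state the rule applied to them: the same failing fraction as in BIOFLOW-V, with all historical Orsiro leavers failing as the extreme.

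The cost is a wording change, a little reprogramming and reruns on data that SAP section 3 already merges into one dataset. The reported tipping point may be less favourable. The primary analysis does not change.

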## 2.7 Analysis of Primary Endpoint

This study will assess non-inferiority of the 12-month TLF rate for the Orsiro stent vs. the Xience stent. The analysis will be carried out on the ITT set (primary), modified ITT and PP analysis sets. The null hypothesis  $H_0$  is that the Orsiro stent will have a primary endpoint (12-month TLF) rate equal to or exceeding that of the Xience group by the non-inferiority margin or more. The alternative hypothesis  $H_A$  is that the Orsiro stent will have a 12-month TLF rate less than the Xience group rate plus the non-inferiority margin. The hypothesis is defined as follows:

$$\begin{aligned} H_0: \pi_X^V - \pi_O^V &\leq -\delta \\ H_A: \pi_X^V - \pi_O^V &> -\delta \end{aligned}$$

where  $\pi_O^V$  is the true 12-month TLF rate for the Orsiro stent,  $\pi_X^V$  is the true 12-month TLF rate for the Xience arm, and  $\delta$  is the non-inferiority margin chosen to be 0.0385 (or 3.85%) as noted in section 2.5.2, Non-Inferiority Margin.

The proposed model is a Bayesian hierarchical model that assumes a bias between the 12-month TLF rates in BIOFLOW-II and BIOFLOW-V as well as BIOFLOW-IV and BIOFLOW-V studies.

Estimation of the parameters and hypotheses testing of the primary hypotheses is based on the posterior distribution of the parameters. The posterior distribution for parameters which do not have closed form posterior inferences will be carried out by sampling from the posterior distribution of the parameters. The freely available program OpenBUGS (Bayesian inference using Gibbs Sampling) will be used to obtain samples from the posterior distribution of the parameters. Using OpenBUGS, 100,000 samples will be obtained from the posterior distribution of 12-month TLF rates after the initial 5,000 will be discarded. To decrease autocorrelation, only every tenth sample will be used in calculations.

We will check convergence of the MCMC sampler using the Brooks-Gelman-Rubin method. Convergence of the sampler will be established if the ratio of within-chain and between-chain variability for multiple chains starting at different initial values will be close to 1.

The percent of posterior samples that satisfy  $\pi_X^V - \pi_O^V > -\delta$  will be used to estimate the posterior probability of the alternative hypothesis will be calculated and reported in the table below.

Table reporting the posterior probability of the Alternative Hypothesis:

Alternative Hypothesis	Posterior Probability
Orsiro is non-inferior to Xience ( $\pi_X^V - \pi_O^V > -\delta$ )	XX.X%

This probability will be contrasted against  $\pi^* = 0.975$  as outlined in Section 2.4.

In addition the posterior means and standard deviations of the parameters will be reported along with 95% Credible Intervals as outlined in the table below.

Table reporting the posterior summaries of the 1-year TLF rates in BIOFLOW-V:

	Mean	SD	Lower Bound 95% Credible Interval	Upper Bound 95% Credible Interval
$\pi_X^V$	X.XX	X.XX	X.XX	X.XX
$\pi_O^V$	X.XX	X.XX	X.XX	X.XX

In addition, an adjusted Bayesian analysis based on multivariable hierarchical logistic regression adjusted for age, diabetes, history of PCI, ischemic status and LVEF will be performed. Treatment effect with logistic regression is expressed on the log ODDS ratio scale. The value of non-inferiority margin used for the non-inferiority test on the log ODDS scale in the adjusted analyses is obtained by transforming the probability-scale non-inferiority margin of 0.0385 to the log-odds scale. The transforming is achieved using the formula:

$$\log\{(0.07 + 0.0385) / (1 - 0.07 - 0.0385)\} - \log\{0.07 / (1 - 0.07)\} = 0.481$$

Thus, for the adjusted analyses, the non-inferiority will be met if

$$P(\text{logit}(\pi_X^V) - \text{logit}(\pi_O^V) > -0.481 | \text{Data}) > 0.975$$

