BIOFLOW-II is a prospective, multicenter, randomized, controlled, non-inferiority trial that enrolled 458 and randomized 452 evaluable subjects at 24 clinical centers in 8 European countries (clinicaltrials.gov identifier NCT01356888). The purpose of this trial was to compare the Orsiro SES with the Xience Prime™ Everolimus Eluting Stent (EES) in subjects with single *de novo* coronary artery lesions in up to two coronary arteries of 2.25–4.0 mm in diameter. Subjects were randomized in a 2:1 fashion to receive the Orsiro stent or the Xience Prime™ stent. All subjects underwent repeat angiography at 9 months post-index procedure. A subset of approximately 60 pre-specified subjects underwent IVUS examination at both baseline and 9 months. Another subset of approximately 60 pre-specified subjects underwent OCT examination at both baseline and 9 months. The primary efficacy endpoint was late lumen loss at 9 months post-index procedure. The first subject was enrolled in July 2011 and enrollment was completed in March 2012. Subjects continue in the follow-up phase of the trial.

Of the 452 enrolled subjects, 298 subjects were randomized to receive the Orsiro stent and 154 were randomized to receive the Xience Prime™ stent. Follow-up angiography was completed in 85% of subjects at 9 months post-procedure and demonstrated a mean in-stent late lumen loss of 0.10 ± 0.32 mm for the Orsiro stent compared to 0.11 ± 0.29 mm for the Xience Prime™ stent. The non-inferiority hypothesis was confirmed with a *P* value of < 0.0001 (delta = 0.16 mm).

At 12 months, clinical event rates were low, and there were no significant differences between the two arms. TLF, a composite measure of safety (target vessel MI, cardiac death) and stent efficacy (clinically-driven TLR and emergent CABG) was measured in the BIOFLOW-II trial. The TLF rate was evaluated, with Kaplan Meier estimates to be 6.5% in the Orsiro group compared to 8.0% in the Xience Prime™ group at 12-month follow-up (log-rank = 0.5832).

The BIOFLOW-II IVUS/OCT subset analyses showed comparable results between the Orsiro and Xience Prime™ groups at 9 months. IVUS results at 9 months demonstrated complete stent apposition (no cases of stent malapposition) in both arms and a significantly lower neointimal hyperplasia area for Orsiro compared with the Xience

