8.8. Analysis of Primary Endpoint

Bayesian analyses will be performed using OpenBUGS⁴⁹ version 3.2.2 or higher. This study will assess non-inferiority of the 12-month TLF rate for the Orsiro stent vs. the Xience stent. The analysis will be carried out on the ITT set (primary) and PP analysis sets.

The null hypothesis is that the Orsiro stent will have a primary endpoint (12-month TLF) rate equal to or exceeding that of the Xience group by the non-inferiority margin or more.

The alternative hypothesis is that the Orsiro stent will have a 12-month TLF rate less than the Xience group rate plus the non-inferiority margin.

$$H_0: \pi_X^V - \pi_O^V \leq -\delta$$

$$H_A: \pi_X^V - \pi_O^V > -\delta$$

where π_0^V is the true 12-month TLF rate for the Orsiro stent, π_X^V is the true 12-month TLF rate for the Xience arm, and δ is the non-inferiority margin chosen to be 0.0385 (or 3.85%).

Due to the randomized nature of the study, we do not expect the two treatment groups to differ on clinically important baseline characteristics, therefore no adjustment is proposed in the primary analysis.

The proposed model is a Bayesian hierarchical model that assumes a bias between the 12-month TLF rates in BIOFLOW-II and BIOFLOW-V as well as BIOFLOW-IV and BIOFLOW-V studies. Full details will be provided in the SAP.

Center heterogeneity

To assess consistency of treatment effect size across study centers, Bayesian models will be employed for the subject level data. Any study center with less than 5 subjects per treatment group will be pooled with other study centers by geographic region prior to carrying out this assessment.

Individual data, for treatment i , study j and individual k will be assumed to follow a Bernoulli distribution:

$$Y[i, j, k] \sim \text{dbern}(p[i, j, \text{center}[k]])$$

where center is an index variable that indicates the center that the individual k was recruited in.

The assumptions are based on a similar model to the model proposed in Legrand et al. 2005.⁵⁰ The event rate is assumed to have an additive effect for center that varies with study:

$$\text{logit}(p[i, j, \text{center}[k]]) = \delta[\text{center}[k]] + (\text{beta}[j] + \gamma[\text{center}[k]]) * (TRT_k = i)$$

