### 2.5 Sample Size Determination

The BIOFLOW-V trial will assess non-inferiority of the 12-month TLF rate for the Orsiro stent vs. TLF rate in subjects treated with the Xience stent. The null hypothesis  $H_0$  is that the Orsiro stent will have a primary endpoint (TLF) rate equal to or exceeding that of the Xience group by the non-inferiority margin or more. The alternative hypothesis  $H_A$  is that the Orsiro stent will have TLF rate less than the Xience group rate plus the non-inferiority margin. Specifically:

$$\begin{aligned} H_0: \pi_X^V - \pi_O^V &\leq -\delta \\ H_A: \pi_X^V - \pi_O^V &> -\delta \end{aligned}$$

Where  $\pi_O^V$  is the true 12-month TLF rate for the Orsiro stent,  $\pi_X^V$  is the true 12-month TLF rate for the Xience arm, and  $\delta$  is the non-inferiority margin.

The assumptions for this analysis are:

- True 12-month TLF rate is 7.0% in both treatment groups ( $\pi_X^V = \pi_O^V$ ).
- Power is 89%.
- 3.85% is the absolute non-inferiority margin (55% relative non-inferiority margin).
- Discount the results of the BIOFLOW-IV data by 20% and BIOFLOW-II data by 30%.
- Standard deviation of the bias terms between the odds of BIOFLOW-II TLF 12-month rates and odds of BIOFLOW-V 12-month rates is 0.3.
- Standard deviation of the bias terms between the odds of BIOFLOW-IV TLF 12-month rates and odds of BIOFLOW-V 12-month rates is 0.3.
- Non-inferiority assessment will be assessed using the posterior probability of the alternative hypothesis as specified above, where  $\pi^* = 0.975$

Rejection of the null hypothesis signifies that the Orsiro stent is not inferior to the Xience stent with regards to 12-month TLF. A total of 1,200 subjects (800 in the Orsiro group and 400 in the Xience group) will have 89.6% power to reject the above null hypothesis in favor of the alternative under the stated assumptions. To account for loss to follow-up (expected to be approximately 10%), a total of 1,334 subjects will need to be randomized. The one-sided type I error estimates are 4.0%, 3.3%, and 4.2% if the actual odds for the 12-month TLF rate of event in the Xience group of the BIOFLOW-IV study are the same, 10% lower and 10% higher when compared with the odds for the 12-month TLF rate of event in the Xience group of the BIOFLOW-V study.

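### The adjusted analysis is judged against a fixed log-odds margin of 0.481, which equals 3.85 points only at a 7% Xience rate and costs about 21 points of power even there

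*SAP*

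**What the plan says.** SAP 2.4 and 2.7 define success on the absolute difference in BIOFLOW-V 12-month TLF rates, with a margin of 0.0385 and a posterior probability threshold of 0.975. Protocol 8.8 leaves the primary analysis unadjusted ("therefore no adjustment is proposed in the primary analysis").

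SAP 2.7 then adds a hierarchical logistic model adjusted for age, diabetes, history of PCI, ischemic status and LVEF. On its margin it says: "The value of non-inferiority margin used for the non-inferiority test on the log ODDS scale in the adjusted analyses is obtained by transforming" the 0.0385 margin to the log-odds scale. The conversion is printed once, with 7% as the Xience rate, and gives 0.481. A decision rule follows: "Thus, for the adjusted analyses, the non-inferiority will be met if" the posterior probability that logit(π_X) − logit(π_O) exceeds −0.481 is above 0.975.

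The SAP does not re-anchor 0.481 at the observed rate, states no power for this test, and does not say how a disagreement with the primary analysis should be read.

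The exponential time-to-event model in SAP 2.8 is handled differently. It is fitted on the log-hazard scale, but its hazards are converted to 12-month rates: "The non-inferiority condition will be expressed in terms of 1-year TLF rates in the BIOFLOW-V study as with the primary hypothesis".

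**The concern.** There are two separate problems.

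First, a fixed log-odds margin corresponds to a different risk difference at every Xience rate. SAP 2.5.2 justifies only an absolute 3.85-point margin. The adjusted rule is stricter than that below 7% and looser above it.

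Second, even at 7%, where both margins describe the same boundary, the two rules do not have the same power. The loss there comes from the scale, not from a mismatched rate.

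An adjusted analysis is normally read as a check on whether covariates change the answer. Here it can contradict the primary analysis with no covariate imbalance at all. A report of adjusted non-inferiority not met, beside a positive primary result, would invite a false explanation. At high event rates the check would instead be too lenient.

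**Working it through.** **1. The plan's conversion.** logit(0.1085) − logit(0.07) = ln(0.1085/0.8915) − ln(0.07/0.93) = −2.106 + 2.587 = 0.481. The SAP's figure is right at 7%.

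**2. Excess tolerated at other Xience rates.** The formula is expit(logit(p) + 0.481) − p. At 8%, the odds are 0.08/0.92 = 0.0870. Multiplied by e^0.481 = 1.618 they become 0.1407, a risk of 12.33%, so the excess is 4.33 points.

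| Xience rate | Excess tolerated (points) |
|---|---|
| 5% | 2.85 |
| 6.6% (BIOSCIENCE, Protocol 3.5) | 3.66 |
| 7% (design) | 3.85 |
| 8.0% (BIOFLOW-II, Protocol 3.5) | 4.33 |
| 10% | 5.24 |

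**3. Why power falls at exactly 7%.** Take equal arms, 800 and 400 subjects, no borrowing, and a normal approximation.

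- Absolute scale: SE = √(0.07 × 0.93 × (1/800 + 1/400)) = 0.01562. Power = Φ(0.0385/0.01562 − 1.96) = 69.3%.
- Log-odds scale: SE = √((1/800 + 1/400)/(0.07 × 0.93)) = 0.2400. Power = Φ(0.481/0.2400 − 1.96) = 51.8%.

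The loss is 17.5 points. The logit is curved: 0.0385/(0.07 × 0.93) = 0.591 on the log-odds scale would be the same number of standard errors from zero as 0.0385 is, but the converted margin is only 0.481.

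**4. With the plan's borrowing.** Inputs from SAP 2.3 to 2.5 and Protocol 8.1:

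- BIOFLOW-V 800/400
- BIOFLOW-IV 370/185 at weight 0.8
- BIOFLOW-II 298/154 at weight 0.7
- bias SD 0.3, taken on the log-odds scale and integrated out
- Beta(1,1) prior, threshold 0.975

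BIOFLOW-II is held at its reported rates (19/298 and 12/154 events); the other studies are simulated. There were 20,000 replicates per cell.

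Check against the plan at 7%: simulated power is 89.5%, and the SAP says 1,200 subjects "will have 89.6% power to reject the above null hypothesis in favor of the alternative under the stated assumptions". One-sided error is 3.8%, against a stated 4.0%.

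Results with equal true rates:

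| Rate in both arms | Power, absolute rule | Power, 0.481 rule | Absolute passes, 0.481 fails |
|---|---|---|---|
| 5% | 97.5% | 62.2% | 35.3% |
| 7% | 89.5% | 68.6% | 20.8% |
| 8% | 84.2% | 71.4% | 12.8% |
| 9% | 78.7% | 74.2% | not tabulated |
| 10% | 73.0% | 76.3% | 1.1% (reverse 4.4%) |

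The power curves cross between 9.4% and 9.6%.

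**5. Passing a true 3.85-point excess** (range over separate runs):

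| Xience rate | Absolute rule | 0.481 rule |
|---|---|---|
| 7% | 3.5–4.3% | 3.1–3.8% |
| 8% | 3.4–4.0% | 5.1–5.9% |
| 10% | 2.9–3.3% | 9.8–10.2% |

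Within each run at 7% the 0.481 rule passed slightly less often.

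**6. Sensitivity of the loss at 7%.** With BIOFLOW-II at its 287/148 twelve-month completers the loss is 19.6 points. If BIOFLOW-II is simulated at the BIOFLOW-V rates, power is 86.3% against 63.5%, a loss of 22.8 points.

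**7. With covariates in the model.** Five covariates were given a combined prognostic SD of 0.5 on the log-odds scale (2,000 replicates, Monte Carlo SE about 1 point). The comparison is the 0.481 rule against a 3.85-point test on standardised risks.

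- 7%: 66.5% against 89.0%
- 8%: 70.4% against 84.5%
- 10%: 76.1% against 73.2%
- 7% with SD 1.0: 63.2% against 90.4%

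Conditioning on covariates also shifts the margin slightly: 3.85 points at 7% becomes a conditional log odds ratio of 0.491 (SD 0.5) to 0.525 (SD 1.0). This is secondary.

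**The case against.** The strongest reply is that no trial decision depends on this rule. Success is defined on the absolute difference, the adjusted analysis is an addition, and the stated 89.6% power belongs to the primary test. Low power in a supportive test produces no false claim, and at the design rate the 0.481 rule is not more permissive. All of that stands, and it limits the severity.

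The scale and its 7% anchor are also disclosed, and SAP 2.5 describes the margin as 55% relative as well as absolute, so a margin that tightens at lower event rates can be defended. Disclosure does not remove the difficulty, because the SAP still declares non-inferiority met or not met on a scale with different operating characteristics.

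The sizes are conditional. Holding BIOFLOW-II at its observed rates is an assumption, and the 1-in-5 figure needs truly equal arms near 7%. Discordance is about 5% if the truth matches BIOFLOW-II (6.5% Orsiro, 8.0% Xience) and about 23 to 25% if it matches BIOSCIENCE (6.5% and 6.6%). The Xience TLF rates that the protocol reports are 6.6% and 8.0%, so the 10% case is an illustration, not an expectation.

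The exponential model has no covariates, so its conversion to risks is immediate, whereas a logistic model needs a standardisation step. The precedent therefore covers the margin, not the method. Finally, LVEF is not listed in the schedule of events or baseline evaluations (Protocol 7.1, 7.2), so it may be missing for some subjects. That is a real gap, but it affects the SAP's own adjusted model equally.

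**Conclusion.** The concern holds, as a matter that should be corrected but does not threaten the primary result. The 0.481 margin equals 3.85 points only at 7%. At the SAP's design assumption ("True 12-month TLF rate is 7.0% in both treatment groups") the rule loses about 21 points of power with the plan's borrowing. The loss is 17.5 points without borrowing and about 23 if BIOFLOW-II shares the BIOFLOW-V rates. About one trial in five would then show a positive primary and a failed adjusted test for reasons of scale alone.

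Looser above 7% describes the margin and the false-pass rate. With equal arms the rule stays less powerful until about 9.5%.

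The simulated sizes assume that the adjusted model borrows as the primary does, that all historical subjects are eligible, and that BIOFLOW-II sits at its reported rates. Covariate prevalences and strengths are also assumed. The drift in the margin is arithmetic and needs none of these.

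**What to change.** Keep the adjusted hierarchical logistic model and its covariates, and replace the 0.481 rule in SAP 2.7 with text such as:

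> For each posterior draw, π_X and π_O are the mean predicted 12-month TLF risks over all BIOFLOW-V subjects in the analysis set, with treatment set to Xience and then to Orsiro. Adjusted non-inferiority is met if P(π_X − π_O > −0.0385 | Data) > 0.975.

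Report the adjusted log odds ratio with its 95% credible interval descriptively, and state that the analysis is supportive. The same paragraph should say how subjects with missing covariates, LVEF in particular, enter the model and the averaging.

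The cost is one SAP paragraph and a few lines of post-processing of the posterior draws, plus whatever handling of missing covariates the adjusted model needs in any case. No new data are required. In the covariate simulation (SD 0.5, no missing covariates) the standardised test had 89.0% power at 7% and passed a true 3.85-point excess 4.2% of the time, close to the plan's 89.6% and 4.0%.
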